Official Title: Duration of Brace Wear in Clubfoot Treatment – A Prospective Randomized Trial

NCT Number: NCT01551264

Document Date: December 30, 2011

Duration of Brace Wear in Clubfoot Treatment – A Prospective Randomized Trial

RESEARCH DESIGN AND METHODS

Aim 1

- a. Establish the time dependent risk for relapse with need for further therapy in isolated clubfoot for 2 year versus 4 year bracing.
- b. Determine whether covariates that include compliance with bracing, gender, age, severity, and family history are associated with relapse.

Rationale

Based on the hypothesis that prolonged bracing will reduce clubfoot recurrence, we propose a multi-center, randomized, controlled trial evaluating the effectiveness of a 2 year versus 4 year bracing protocol in preventing clubfoot recurrence. No studies have previously assessed the length of bracing necessary to prevent clubfoot recurrence; therefore, the results of this study will have great clinical utility. When designing this trial, we sought to balance rigor with feasibility, and to maximize internal validity without sacrificing external validity.

Sample Size Justification and Statistical Power

The primary goal of this project is to determine the rate at which clubfoot recurs during the first year post-treatment. Because this primary goal involves estimation, we discuss sample size issues from the perspective of confidence bounds. *Table 1 presents the statistical power to detect between-group differences for various recurrence rates with the target enrollment sample size of 62 patients per group. Assuming a 10% dropout rate, with a total enrollment of 124 patients (55/group completing the entire trial) and observed recurrence rates of 10% versus 45%, statistical power will be excellent (0.99) to detect this between-group difference in recurrence rate of at least 35%.* That is, with 95% certainty, our estimate of the between-group difference in recurrence rate will be within 15% (50%-20%/2) of the true rate difference. Even with a more conservative estimate of the between-group difference, the study will have adequate power (0.80) to detect a between-group difference as small as 21%; where the recurrence rate in one group is 10% and the recurrence rate in the other group is as small as 31%.

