Study subjects will be seen every 3 months. Interim visits for brace fitting and consultation or family discussions with the physician/coordinator/orthotist will be allowed and encouraged. Local coordinators will contact the patient and family via phone at least monthly to provide the opportunity for questions, discussion, and feedback as needed. Subjects will be evaluated at each visit of the current state of their clubfoot and will be told if there are any signs of recurrence. Parents have the right to withdraw from the study at anytime.

5. Study Endpoint

Although follow-up data will be collected for the duration of the trial, the data collected at 1-year follow-up post completion of treatment arms will be used for the primary analysis to address the question asked in specific aim 1a. This ensures that patients in both treatment arms are followed for the same amount of time after they finish bracing.

6. Statistical Analysis

General

The goal of this study is to establish the time-dependent risk for recurrence within the first year post-treatment and evaluate factors associated with recurrence in isolated clubfoot. Kaplan-Meier survival curves that describe the time to recurrence will be generated, with

95% confidence bounds placed around the probabilities that this event will occur at pre-defined intervals. Of particular interest will be an assessment of the hazard ratio, with 95% confidence bounds, that compares recurrence in patients receiving 2-year versus 4-year bracing. While the goal of this study is to detect an overall treatment difference, Cox regression analysis will determine whether covariates that include compliance with bracing, gender, laterality, age, Pirani score, and family history are associated with the probability that relapse will occur. A separate Cox model will be used for each covariate.

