Additional analyses include mixed model repeated measures analysis of variance to determine if the magnitude of changes in exam findings differs according to whether a recurrence ultimately occurs. Unlike traditional repeated measures analyses, the mixed model method allows for the inclusion of patients with incomplete data. The focus of these analyses will be the interaction between recurrence group and time point; interactions that test hypotheses regarding the equality of changes over time in the two groups. Within the mixed model, appropriate statistical contrasts will be used to test the null hypothesis that changes between two specific time points in one group are equal to corresponding changes in another group.

Simple t-tests and chi-square tests will be used to determine if characteristics at study enrollment differ according to whether there is recurrence. Receiver operating characteristic (ROC) curve analysis will be performed to determine if measures of compliance discriminate patients that recurrence from patients that do not recurrence.

These data will be analyzed with an "intention to treat" principle; wherein patients will be included in the intervention group as determined by the randomization, independent of compliance. Secondary analyses will be performed to evaluate the effects of treatment independent of crossover by examining outcomes relative to actual treatment status.

For all analyses, careful attention will be given to whether the data satisfy the distributional and model-specific assumptions of the procedures used. Appropriate data transformations or non-parametric methods will be used as appropriate.

It is important to point out that this study is not designed to (1) assess the safety or efficacy of a particular brace; (2) compare outcomes across clinical sites. All sites will use foot abduction braces. To avoid any perception of conflict of interest and to follow recommendations from the Disclosure Review Committee, the type of particular brace used will not be recorded in the study data. Brace type is inherently associated with clinical site and site physician. As such, the following variables will not be included as effects of interest in the analytic models: brace type, clinical site, physician, and orthotist.

Heat sensor data (analysis)

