While previous studies by our group and others have demonstrated that brace noncompliance is the number one risk factor for recurrence (Dobbs et al. 2004), these conclusions were made without objective measures of brace compliance. In prior studies, brace dose has been addressed simply as "compliance" or as an average number of hours worn.

Because we will use a heat sensor to objectively and accurately monitor compliance, compliance may be evaluated as both a continuous and a dichotomized measure. First, we will calculate the area under the curve to create one summary measure per patient per study period (or across the entire intervention period) as a continuous variable (i.e. average hours worn). For each individual, an area under the hours worn curve will be computed and the areas compared across between groups of patients who recurrence and those who do not. Second, we will analyze compliance as a dichotomized variable. For example, an adherer is someone who wears the brace for at least 80% of the prescribed time. The percentage of each group (recurrent patients versus non-recurrent group) who adhere to bracing regimen during each study time period (or across the entire intervention period) will be compared. Simple t-tests will be used to compare each group.

7. Data Management and Quality Control Activities

The first three months of this study will be spent establishing the infrastructure necessary to assemble data. **[The coordinator will need time to train personnel at participating site].** Prior to study start, the Coordinating Center (CC) will develop a data quality assurance plan and develop quality control procedures (QC) in accordance with the plan. The CC Research Coordinator will develop a Manual of Procedures (MOP) to address enrollment, patient safety monitoring, adherence to study procedures and timelines, and to facilitate consistency in protocol implementation and data collection across clinical sites. The MOP will specify the methods by which data is to be collected and related quality assurance procedures. The CC Coordinator will also provide dynamic training and certification of personnel across sites to ensure standardization of procedures.

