An "as-treated" analysis will be performed in addition to the primary intention-to-treat analysis to take into account the effect of crossover and dropout. It should be remembered that crossover occurs in the typical clinical setting whenever the patient either doesn't wear the brace at all, wears the brace at a less-than-effective dose, or when the patient or physician requests a brace after a period of observation. If a subject crosses over from observation to bracing treatment, we will be able to account for the patient's characteristics at the time of cross-over, and the dose monitor will allow measurement of subsequent time in brace. A 10 percent lost-to-follow-up rate has been taken into account in the sample size/power calculations. Although unrealistic, only a 0% rate of loss to follow-up guarantees the benefits of randomization. We will employ several proven strategies to minimize loss to follow-up, including education concerning the full burden of trial participation, minimization of respondent burden in terms of visits and questionnaires, obtaining at least one alternative contact for each subject, as well as phone calls and other reminders of upcoming visits. The seven centers have a documented ability to cover a 15% rate of dropout that is 5% greater than the estimate used for planning purposes. If dropouts exceed this during the recruitment phase, then centers from the alternate list will be brought into the study. If excessive dropouts occur during the follow-up phase of the study, no additional centers will be recruited and instead, attempts to locate the patient and determine final outcome will be made, and if needed, statistical methods will be employed to compensate for missing data.

Summary of Research Proposal

Clubfoot is a common and severe musculoskeletal birth defect. Although clubfoot is often successfully treated with the Ponseti method, some clubfeet relapse in the following years. One goal of this study is to provide clinically useful information regarding the optimal length of abduction bracing that is necessary to prevent clubfoot recurrence. A second goal of this study is to investigate the other variables (clinical, bracing compliance) that influence clubfoot recurrences. These studies have great potential to impact the care and treatment of patients with clubfoot.

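### Aim 1b never adjusts the compliance hazard ratio for severity or age, and the plan does not say whether the randomised arm is in the models

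*Combined protocol and SAP*

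**What the plan says.** Aim 1, part b, reads: "Determine whether covariates that include compliance with bracing, gender, age, severity, and family history are associated with relapse". Section 6 (Statistical Analysis, General) gives this to Cox regression, which is to show whether "covariates that include compliance with bracing, gender, laterality, age, Pirani score, and family history are associated with the probability that relapse will occur". The next sentence fixes the form: "A separate Cox model will be used for each covariate".

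The other covariate analyses also take one variable at a time. Under General these are t-tests, chi-square tests and ROC curves. Under Heat sensor data (analysis), the sensor output is used to "create one summary measure per patient per study period (or across the entire intervention period) as a continuous variable". Recurrent and non-recurrent patients are then compared on it and on the share of adherers, ending with "Simple t-tests will be used to compare each group". No adjusting variable is named.

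Four other places bear on the point:

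- General says that "the following variables will not be included as effects of interest in the analytic models: brace type, clinical site, physician, and orthotist". The randomised arm is not on that list, and nothing says that it is in the Aim 1b models.
- The Summary of Research Proposal puts the purpose more strongly: "A second goal of this study is to investigate the other variables (clinical, bracing compliance) that influence clubfoot recurrences".
- Under Possible outcomes, item 1 (Patient Enrollment), a contingent observational cohort would be analysed with propensity scores, because its groups are not formed by randomisation.
- Item 2 there (Crossovers, Dropouts, and Subjects Lost to Follow-Up) says that patient characteristics at crossover can be accounted for in the as-treated work, but names no model.

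**The concern.** Brace wear is observed after randomisation and is not assigned. If children with more severe feet are worn less and also relapse more, a Cox model with compliance alone credits compliance with part of the effect of severity. If severe feet are worn more, the same model can hide a real benefit of wear. The heat sensor removes error in measuring wear; it does not remove confounding.

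The handling of arm matters for a separate reason. Section 3 sets night-time bracing at 2 or 4 years by arm, so a compliance summary over the whole period covers a different span in each arm. If average wear differs between arms, a model without arm mixes the compliance effect with the randomised effect.

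At stake is the reading of the Aim 1b compliance result. The remedy needs only data that section 2 (Randomization and Data Collection) already collects.

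**Working it through.** **Inputs from the documents.** 62 enrolled and 55 complete per group; 10% dropout; two-sided alpha 0.05; recurrence 10% v 45%, 40% or 31% (Table 1); six covariates (section 6). The documents give no power or event count for Aim 1b.

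**Assumptions not in the documents.** Severity hazard ratio (HR) 1.5 or 2.0 per SD; severity-compliance correlation 0 to -0.5, with one run at +0.3; true compliance HR 1.0 or 0.6 per SD.

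**Step 1: reproduce Table 1.** Power = Φ{[d√n − 1.96√(2p̄q̄)] / √(p1q1 + p2q2)}, with n = 55 and p1 = 0.10.

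- p2 = 0.45: (2.596 − 1.238)/0.581 = 2.34, power 0.990 (plan 0.99)
- p2 = 0.40: (2.225 − 1.200)/0.574 = 1.78, power 0.963 (plan 0.96)
- p2 = 0.31: (1.557 − 1.119)/0.551 = 0.80, power 0.787 (plan 0.80; 0.807 with unpooled variance)

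Table 1 reproduces.

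**Step 2: events available.** 55 × (0.10 + 0.45) = 30.25 and 55 × (0.10 + 0.31) = 22.55. Six covariates plus arm: 22.55/7 = 3.2 to 30.25/7 = 4.3 events per term. Three terms: 22.55/3 = 7.5 to 30.25/3 = 10.1. Recurrences during bracing would add events, but the documents give no rate for them.

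**Step 3: no true compliance effect.** Simulated trials with 55 per arm, exponential times matched to the Table 1 rates at 1 year, and compliance = r × severity + noise. There were 1,000 trials per row, so the Monte Carlo standard error at 5% is √(0.05 × 0.95/1000) = 0.7 points. Cells give median compliance HR per SD and rejection rate.

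| Severity HR | Rates | Correlation | Compliance alone | With severity and arm |
|---|---|---|---|---|
| 2.0 | 10 v 45% | 0 | 1.009, 5.1% | 1.008, 5.4% |
| 2.0 | 10 v 31% | 0 | 0.995, 4.6% | 0.990, 5.5% |
| 2.0 | 10 v 45% | -0.2 | 0.880, 10.4% | 0.989, 5.5% |
| 2.0 | 10 v 31% | -0.2 | 0.879, 8.9% | 0.992, 4.4% |
| 2.0 | 10 v 45% | -0.3 | 0.853, 14.2% | 1.006, 4.9% |
| 2.0 | 10 v 31% | -0.3 | 0.835, 15.4% | 1.025, 6.0% |
| 2.0 | 10 v 45% | -0.5 | 0.745, 36.9% | 0.995, 7.3% |
| 2.0 | 10 v 31% | -0.5 | 0.734, 31.5% | 0.993, 4.9% |
| 1.5 | 10 v 45% | -0.3 | 0.888, 10.0% | 0.996, 6.5% |
| 1.5 | 10 v 45% | -0.5 | 0.838, 16.3% | 1.002, 5.2% |

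A separate set of 3,000 trials per cell, over severity HR 1.5 to 2.0 and correlation -0.2 to -0.5, gave 6% to 35% unadjusted (average HR 0.93 to 0.73). Stratified by arm with severity added, it gave 5% to 6% (HR 1.00). Adding arm alone does not help with severity: at correlation -0.5, severity HR 2.0 and 10 v 45%, rejection with arm but not severity was 42.2%.

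**Step 4: true compliance HR 0.6, severity HR 2.0.** Rejection rates:

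| Rates | Correlation | Compliance alone | With severity and arm |
|---|---|---|---|
| 10 v 45% | 0 | 60.9% | 78.8% |
| 10 v 31% | 0 | 58.6% | 66.6% |
| 10 v 45% | -0.3 | 86.2% | 71.3% |
| 10 v 31% | -0.3 | 83.1% | 59.8% |
| 10 v 45% | -0.5 | 94.4% | 65.8% |
| 10 v 31% | -0.5 | 92.6% | 51.9% |
| 10 v 45% | +0.3 | 27.6% | 76.2% |

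**Step 5: arm.** Let the compliance measure differ by 0.5 SD between arms, have no effect and be uncorrelated with severity (10 v 45%). The model without arm rejects in about 17% of trials in either direction (HR 0.833 or 1.187); with arm it rejects in about 5%. For a baseline covariate with HR 1.5 per SD (62 per arm, 10% random dropout), stratifying by arm raises power from 0.54 to 0.62 at 10 v 45% (gain 0.08) and from 0.48 to 0.50 at 10 v 31% (gain 0.02).

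**The case against.** **The aim is association only.** Aim 1b and section 6 speak of association, and one-covariate models estimate that. With about 23 to 30 events, simple models for a second goal are defensible. This stands as a reason to keep those results and to avoid a seven-term model. It does not remove the point: the Summary asks which variables influence recurrence, and the plan itself adjusts for non-randomised choice in its contingent cohort.

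**The arm is not shown to be omitted.** A reader might infer that the models exclude the arm. The wording fits arm plus one covariate as well as one covariate alone, and the list of excluded variables does not include arm. The supportable statement is that the plan does not say.

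**Lost power is not the general fault.** A reader might infer that separate models always lose power. For baseline covariates the loss arises only if arm is omitted, and it is small. When severe feet are worn less, the unadjusted compliance test rejects more often, not less (86.2% v 71.3% at -0.3, 10 v 45%), and part of that excess is bias.

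**The size is assumed.** The documents give neither the correlation nor its sign. Section 3 requires every foot to reach set correction thresholds before bracing, which makes a strong link between initial Pirani score and wear less certain. This stands.

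**Adjustment is incomplete.** In the simulations severity is the only confounder, so adjusting for it must return an HR near 1. With an added unmeasured factor (HR 1.5, correlation -0.3 with compliance; severity the same; 1,500 trials, 55 per arm), rejection was 22% unadjusted (HR 0.82) and still 11% adjusted (HR 0.88). Adjustment halves the error but does not remove it. Nor does it settle how a whole-period summary treats wear after a recurrence, which section 3 follows with casting and further bracing.

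**Conclusion.** The point holds as a worthwhile improvement to a secondary aim. As written, compliance is never adjusted for Pirani score or age in the randomised cohort, and the role of arm is unstated. The fault is possible bias in either direction.

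Over severity HR 1.5 to 2.0 and correlation -0.2 to -0.5, false rejection is roughly 6% to 37%, against 4% to 7% after adjustment for severity and arm. With zero correlation, and wear equal between arms, there is no bias. The textual reading is firm; the size depends wholly on those assumptions. The simulated models did not include age.

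A reader might also infer that the trial's main result is at risk. It is not: the primary log-rank comparison and the Table 1 power do not depend on these models.

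**What to change.** Replace the sentence in section 6 with:

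> All Aim 1b Cox models are stratified by randomised arm. The main compliance result comes from one pre-specified model containing compliance, Pirani score and age at treatment initiation; one-covariate hazard ratios are reported as descriptive.

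Stratifying by arm uses no coefficient, so the model has three terms. All the variables are already collected, so the change is to wording only.

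The costs are:

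- a wider interval and a lower rejection rate for compliance when it is correlated with severity, which at correlation -0.5 is a large drop (Step 4);
- a model that is still fairly thin, at about 7 to 10 events per term at the Table 1 rates;
- control of measured confounders only, and of the two named ones at that. Family history stays outside the model, and the adjusted result should not be called causal.

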are not fully corrected will undergo further casting until correction is achieved before starting the bracing protocol. The number of casts required to achieve correction will be recorded as well as any casting complications. After achieving correction all patients are fitted **with a foot abduction brace (FAB) consisting of shoes attached to a bar**. The type of FAB used will be based on physician and family preference but the common factor between all braces will be the presence of a bar connecting the shoes. The presence of a bar has been shown to be the crucial feature of clubfoot bracing (Janicki 2011). All caregivers will be instructed to place child in the FAB 23 hours a day for three months and then night time use (eight to twelve hours) hours a day for 2 versus 4 years based on treatment arm. All braces will include an implanted temperature logger that will be launched by the research coordinator prior to mounting.

All centers will provide the names and credentials of the orthotists they plan to work with for the study. The orthotist will adjust pads, areas of relief, and straps as needed to optimize fit. Clubfoot recurrence will be determined by the treating physician and treated with repeat casting followed by FAB use. Recurrence is defined as the development of any of the following deformities in isolation or in combination that require repeat cast application or surgical intervention: hindfoot varus, hindfoot equinus, forefoot adduction, forefoot cavus, or forefoot.

The Coordinating Center will develop manuals of operations to standardize patient management. However, variability in practices is allowed and will be at the discretion of the physician and orthotist at each clinical site. This may impart some variation in care across the centers, but will realistically mimic the current state of the art for the best care possible. Randomization within sites will minimize the potential bias introduced by differences in patient populations and management across sites and orthotists

4. Follow-Up Schedule

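### The mixed model of exam findings groups children by later recurrence without excluding the recurrence visit or visits after re-casting, so its group-by-time test can be significant without any predictive content

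*Combined protocol and SAP*

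**What the plan says.** **The analysis.** In section 6, Statistical Analysis (General), among the additional analyses, the plan proposes mixed-model repeated measures "to determine if the magnitude of changes in exam findings differs according to whether a recurrence ultimately occurs". It continues: "The focus of these analyses will be the interaction between recurrence group and time point". Contrasts within the model will test whether "changes between two specific time points in one group are equal to corresponding changes in another group". The time points are not named, and the term for exam findings is not defined.

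**The grouping variable.** Section 3, Casting and Bracing Protocol, defines recurrence as the development of any "deformities in isolation or in combination that require repeat cast application or surgical intervention: hindfoot varus, hindfoot equinus, forefoot adduction, forefoot cavus, or forefoot". On who decides and what follows, it says: "Clubfoot recurrence will be determined by the treating physician and treated with repeat casting followed by FAB use".

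**The examinations.** Section 4, Follow-Up Schedule, says: "Study subjects will be seen every 3 months". It adds: "Subjects will be evaluated at each visit of the current state of their clubfoot and will be told if there are any signs of recurrence". Section 5, Study Endpoint, has follow-up data collected throughout the trial.

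None of these sections limits the mixed model to visits before recurrence, sets a landmark time, or says how visits after repeat casting are handled.

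**The concern.** There are two separate difficulties.

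1. **Selection on the outcome.** A child joins the recurrence group because deformity reappeared at an examination. If the modelled findings include those deformities, or a score built from them, the recurrence group must look worse at its recurrence visits. The null hypothesis of equal change is then false by construction, whatever the earlier findings show.
2. **Mixed states at one visit.** Recurrence is treated by repeat casting. At a given visit the recurrence group can hold feet that have not yet relapsed, feet that are relapsing, and feet that have been corrected again. An average over these has no clear meaning, and treatment can move it either way. This applies to any finding that re-casting changes, even one outside the recurrence definition.

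At stake is how this additional analysis is read. A significant interaction could be taken as evidence that a particular pattern of exam change warns of recurrence, when it may only restate the definition of recurrence or show the effect of re-casting.

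**Working it through.** **Plan's own figures.** The plan gives no figure for the mixed model. Its only power figures (0.99, 0.96 and 0.80 in Table 1) concern the comparison of recurrence rates between arms. With 55 per group and a pooled two-proportion test they recompute as 0.990, 0.963 and 0.787. They have no bearing on this point.

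**Number of visits.** Visits are 3-monthly, which is 4 a year. Bracing lasts 2 or 4 years, and the primary endpoint is 1 year after it ends.
- 2-year arm: (2 + 1) x 4 = about 12 follow-up visits.
- 4-year arm: (4 + 1) x 4 = about 20 follow-up visits.

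**Simulation inputs.** From the plan: 2 x 55 = 110 children with complete data. All else is assumed:
- score = child effect (SD 0.5) + independent visit noise (SD 1), with no trend;
- recurrence = first follow-up score above a threshold set to give 10-30% recurrence, so the score alone decides recurrence;
- baseline visit included and all visits kept.

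Because the visit noise is independent and there is no trend, a child's change between earlier visits carries no information about later recurrence.

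**Test.** Subtract each child's own mean, then compare residual sums of squares with common visit means (RSS0) and with separate visit means by recurrence group (RSS1):

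F = [(RSS0 - RSS1)/(K - 1)] / [RSS1/((N - 2)(K - 1))]

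Here N = 110 and K is the number of visits including baseline. For 12 follow-up visits, K = 13, with 12 and 108 x 12 = 1,296 degrees of freedom. For 20, K = 21, with 20 and 108 x 20 = 2,160.

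**Rejection at nominal 5%, across 10-30% recurrence:**

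| Follow-up visits | Re-casting has no effect | Re-casting improves later scores by 1 SD |
|---|---|---|
| 4 | 34-40% | 51-61% |
| 8 | 17-23% | 63-84% |
| 12 to 20 | 11-22% | 74-99% |

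The last row matches the trial's schedule. Repeat runs of 2,000 trials per setting, with minor coding differences, gave 9-23% at 12-20 visits without a treatment effect, and 72-94% at 12 visits with the 1 SD effect.

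**Effect of partial overlap.** When the visit noise behind the recurrence decision was assumed to correlate only 0.5 with the noise in the exam score, rejection at 12-20 visits fell to 5-8%.

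**Single contrasts.** A second simulation used 110 children, 13 quarterly visits, no child effect, about 20% recurring, t-tests on change and 1,000 runs.
- Baseline to the recurrence visit, against a matched visit in the others: significant in 100% of runs.
- Baseline to last visit: about 87% if re-casting lowers later scores by an assumed 1.5 SD, and 12-13% with no treatment effect.
- Baseline to an early landmark (visit 3), using later recurrences only: 4-5% with no serial correlation, and 8-10% with serial correlation 0.5. In the latter case earlier findings do carry some information, so the excess over 5% is not an artefact.

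**Check of the remedy.** In the first set-up, limiting the model to visits before the recurrence visit gave 2-5% rejection.

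**The case against.** The case on the other side has real weight.

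- **Overlap is not stated.** The plan does not define the exam findings, and recurrence also needs the treating physician's decision to re-cast or operate. A reader might infer that the test is wholly circular. The documents do not support that: strong overlap is a reasonable inference from the per-visit assessment of the clubfoot, but it is not written down and need not be complete. The 5-8% result shows how much depends on it.
- **Retention of later visits is not stated.** A reader might infer that the plan puts post-recurrence visits into this model. It says only that data are collected throughout the trial. The contrasts could be chosen before recurrence. What stands is that later visits are not excluded.
- **The size is modest on the trial's own schedule.** A reader might take the 34-40% at four follow-up visits as typical. The schedule implies about 12 or 20 visits, where the figure is 11-22%. The much larger figures require an assumed re-casting effect.
- **It is an additional analysis.** Aim 1b names compliance, gender, age, severity and family history, and the plan studies these by Cox regression. Change in exam findings is not on that list, although the closing summary's second goal refers more broadly to clinical variables. The plan does not say that the mixed model is for prediction, and a description of trajectories may be all that is meant.

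These points limit the size and importance of the problem. They do not remove it, because the plan tests a formal null hypothesis and sets no pre-recurrence cut-off.

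**Conclusion.** The point holds in a limited form. As written, the group-by-time interaction can be significant because of how the groups are formed and how recurrence is treated, so it cannot by itself show that exam changes precede or predict recurrence. With a pure-noise score that alone determines recurrence, the nominal 5% test rejects in about 11-22% of trials at 12-20 follow-up visits, and in about 74-99% with an assumed 1 SD improvement after re-casting. These figures are illustrative: the documents supply only the number of children and the visit schedule, and partial overlap can bring the rate close to nominal.

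A reader might extend this to the main result, which the documents do not support. The primary intention-to-treat log-rank comparison of the randomised arms does not use this grouping, and the hazard ratio, sample size and power are unchanged.

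**What to change.** Amend the additional-analyses paragraph in section 6 as follows.

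1. Name the exam measures to be modelled and the time points to be contrasted.
2. Restrict the mixed model to visits before the recurrence visit, excluding that visit and every visit after re-casting. Post-re-casting findings can be described separately.
3. Alternatively, reverse the direction: a Cox model for time to recurrence, with the previous visit's finding as a time-dependent covariate and the child leaving the risk set at recurrence. This answers a somewhat different question, whether a finding at one visit is associated with recurrence afterwards, so the choice depends on what the investigators want to know. Step 2 alone is enough to remove the artefact.

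The cost is SAP wording and, for the Cox option, a slightly more complex model of a type the plan already uses. No new data are needed. The downside is fewer visits per recurring child, and so somewhat less precision in this additional analysis.
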